## Changes to the protocol

Changes to specific sections of the protocol are shown in the track changes version of the protocol using ~~strike through red font~~ for deletions and red underlined for insertions.

The major changes made to the protocol are summarized in this section. Other minor changes are incorporated directly into the protocol. The major changes include the following:

- Phase IIIb study patients not eligible for reimbursement can remain in the study 180 days post fingolimod reimbursement.
  - Patients from CFTY720D2309/E1 can enter the trial and phase II/III patients who previously completed this trial can re-enter for long-term follow-up.
  - Inclusion/Exclusion criteria are updated.
  - First dose monitoring required following interruptions of study drug of greater than 14 consecutive days; previously, following interruption of 8 days or greater.
  - Optional pulmonary function testing (PFT) is added.
  - Skin exams are no longer required; remain as optional.
- 

- OCT and Ophthalmic exam frequency is adjusted.
- EDSS certification requirement added for investigators evaluating Phase II/III patients; collection of functional EDSS scores added for the Phase II/III patients.
- Visit frequency adjusted to every 6 months, starting with Visit 6.
- MRI testing added for Phase II/III patients.
- Definition of “confirmed relapses” is added; the confirmed relapse information is to be collected.
- Several laboratory tests are no longer being collected (HbA1c, HIV, hepatitis B and C, herpes simplex virus 1 and 2, and rubeola).

- 
- Changes to contraception requirements and to safety guidelines for pregnant patients.
  - Changes to safety guidelines for patients with elevated liver function tests, diagnosis of macular edema or basal cell carcinoma.

A copy of this amended protocol will be sent to the Institutional Review Board (IRBs)/ Independent Ethics Committee (IECs) and Health Authorities.

[figure not shown]
The changes described in this amended protocol require IRB/IEC approval prior to implementation. In addition, as the changes herein affect the Informed Consent, sites are required to update and submit for approval a revised Informed Consent that takes into account the changes described in this amended protocol.

## **Amendment 3-May 2011**

### **Amendment rationale**

Study CFTY720D2399 includes patients who previously participated in the fingolimod phase II (D2201) and phase III (D2301, D2302, D2309) studies and their associated extension trials (CFTY720D2201E1, CFTY720D2301E1, CFTY720D2302E1, CFTY720D2309E1). In addition, patients who have participated in and completed ongoing phase IIIb studies of fingolimod are also eligible. Patients who participated in the phase IIIb trials initiated treatment with fingolimod only recently. Patients who were participating in the phase II/III development program have 2-7 years of continuous exposure and met specific inclusion/exclusion criteria and have very well documented clinical course over those years. These latter patients provide valuable long-term data on safety and efficacy of fingolimod treatment, coupled with careful baseline assessments.

The rationale of this amendment is to allow further follow-up of those patients who previously completed the Phase II or III fingolimod clinical development trials in an interventional trial setting through 30-Jun-2016. In addition, this amendment will allow the re-enrollment of those phase II/III patients who have completed participation in one of the phase II/III extension studies, who remain on fingolimod therapy and wish to continue on fingolimod in a clinical trial setting.

Those patients originating from the phase IIIb program will be offered to transition into observational studies to collect long-term safety data in the setting of standard medical practice upon approval and reimbursement of fingolimod in the respective country, as foreseen in the original version of this protocol.

### **Changes to the protocol**

The changes made throughout the protocol update the study end for the Phase II/III patients to fingolimod registration, commercial availability and reimbursement OR through 30-June-2016, whichever is later.

Changes to specific sections of the protocol are shown in the track changes version of the protocol using ~~strike through red font for deletions~~ and red underlined for insertions.

A copy of this amended protocol will be sent to the Institutional Review Board (IRBs)/ Independent Ethics Committee (IECs) and Health Authorities.

The changes described in this amended protocol require IRB/IEC approval prior to implementation. In addition, as the changes herein affect the Informed Consent, sites are required to update and submit for approval a revised Informed Consent that takes into account the changes described in this amended protocol.

## **Amendment 2-March 2011**

### **Amendment rationale**

The rationale for this amendment in Norway is to revise the study endpoint to 01-Aug-2012 is to allow patients who complete ongoing studies to receive continuous treatment with fingolimod and to collect long-term safety data for approximately 12 months following the completion of prior trial. As the study has not yet started in Norway, there is no impact on the patients or the study itself.

Additionally, the Exclusion criterion 10c is updated to be in accordance with the recommended wording in the Summary of Product Characteristics for fingolimod, as agreed upon by CHMP. The exclusion is expanded to arrhythmia requiring current treatment with Class Ia or III antiarrhythmic medications.

### **Changes to the protocol**

The changes made throughout the protocol are specific to Norway and update the study endpoint to reflect the time point approximately 12 months following the completion of the previous fingolimod trial or maximally through 01-Aug-2012.

The References section is updated to correct clerical errors.

Changes to specific sections of the protocol are shown in the track changes version of the protocol using ~~strike through red font for deletions~~ and red underlined for insertions.

A copy of this amended protocol will be sent to the Institutional Review Board (IRBs)/ Independent Ethics Committee (IECs) and Health Authorities.

The changes described in this amended protocol require IRB/IEC approval prior to implementation. In addition, as the changes herein affect the Informed Consent, sites in Norway are required to update and submit for approval a revised Informed Consent that takes into account the changes described in this amended protocol.

## **Amendment 1-July 2010**

### **Amendment rationale**

- The rationale for this amendment in the UK is to revise the study endpoint to 31-Dec-2012 to be in line with the Commission Directive 2005/28/EC and the requirements of the UK Health Authority. As the study has not yet started, there is no impact on the patients or the study itself.
- The rationale for this amendment in Poland is to revise the study endpoint to 31-Dec-2012 in order to continue to provide patients treatment through what is considered a reasonable period of time for reimbursement to be achieved in Poland where thereafter patients can, if within their treatment plan, receive commercial supply as prescribed by their physician. As the study has not yet started, there is no impact on the patients or the study itself.

### **Changes to the protocol**

The changes made throughout the protocol are specific to Poland and the UK and update the study endpoint to reflect until fingolimod is registered and through approximately one-year post approval or maximally through 31-Dec-2012.

Changes to specific sections of the protocol are shown in the track changes version of the protocol using red underlined for insertions.

A copy of this amended protocol will be sent to the Institutional Review Board (IRBs)/Independent Ethics Committee (IECs) and Health Authorities.

The changes described in this amended protocol require IRB/IEC approval prior to implementation.

## Protocol synopsis

### Title of study:

A single arm, open-label, multicenter study evaluating the long-term, safety and tolerability of 0.5 mg fingolimod (FTY720) administered orally once daily in patients with relapsing forms of multiple sclerosis.

### Purpose and rationale:

The purpose of this study is to collect long-term safety, tolerability, efficacy, and health outcomes data in patients who participated in the fingolimod multiple sclerosis clinical development program.

### Objectives:

#### Primary Objectives:

This study is designed to evaluate the long-term safety and tolerability of fingolimod 0.5 mg/day in patients with MS for the duration of the study.

#### Secondary Objectives:

This study will also evaluate long-term efficacy of fingolimod 0.5 mg/day in patients with MS, as measured by disability progression, brain volume (atrophy), T1- (non-enhanced) and T2-weighted lesion volume and MS relapse occurrence in Study Part One.

### Population:

Approximately 5000 patients who have completed ongoing or planned clinical trials in the MS development program with fingolimod are expected to be enrolled in >500 centers worldwide.

### Inclusion/Exclusion criteria:

#### Inclusion Criteria:

Patients eligible for inclusion in this study have to fulfill all of the following criteria:

1. Written informed consent must be obtained before any assessment is performed.
2. Patients who have completed designated ongoing or planned Novartis global clinical trials with fingolimod and are unable to obtain fingolimod outside a clinical trial.

#### Exclusion Criteria:

Patients fulfilling any of the following criteria are not eligible for inclusion in this study:

1. Premature permanent discontinuation from any fingolimod study due to:
  - a. An adverse event or serious adverse event or laboratory abnormality.
  - b. Conditions leading to permanent study drug discontinuation.
2. Pregnant or nursing (lactating) women, where pregnancy is defined as the state of a female after conception and until the termination of gestation, confirmed by a positive hCG laboratory test (> 5 mIU/ml). Patients who temporarily or permanently discontinued from any fingolimod study because of pregnancy can be re-enrolled.
3. Women of child-bearing potential, defined as all women physiologically capable of becoming pregnant, UNLESS they are using highly effective contraception during the study and for 2 months after stopping treatment. 'Highly effective contraception' defined as contraception which results in less than 1% unwanted pregnancies when used properly according to the label.

4. Chronic disease of the immune system other than MS which may require immunosuppressive treatment.
5. Severe active infection or active chronic infection.
6. Previous treatment with cladribine, cyclophosphamide or mitoxantrone.
7. Treatment with monoclonal antibodies (including Natalizumab) in the past 3 months.
8. Uncontrolled diabetes (HbA1c>9%).
9. Macular edema at Baseline.
10. Any medically unstable condition that may interfere with the patient's ability to cooperate and comply with the study procedures, as assessed by the treating physician.
11. Any of the following cardiovascular conditions:
  - a. myocardial infarction within the past 6 months prior to enrollment or current unstable ischemic heart disease;
  - b. cardiac failure at time of Screening (Class III & IV, according to New York Heart Association Classification) or any severe cardiac disease as determined by the investigator;
  - c. patients receiving current treatment with Class Ia or III antiarrhythmic drugs (e.g., quinidine, disopyramide, amiodarone, bretylium, sotalol, ibutilide, azimilide, dofetilide, ajmaline, procainamide);
  - d. second-degree AV block Type II or third-degree AV block or corrected QTc interval >450 msec in males or >470 msec in females;
  - e. sick sinus syndrome or sino-atrial heart block;
  - f. uncontrolled hypertension despite prescribed medications.
12. Any of the following pulmonary conditions during the previous fingolimod study or observed at the enrollment visit:
  - a. severe respiratory disease or pulmonary fibrosis;
  - b. active tuberculosis;
  - c. in patients enrolling from studies with regular spirometry: reduction of FEV1, FVC and/or DLCO below 60% of core study baseline values or if FEV1, FVC and/or DLCO at extension study baseline is the second of two consecutive pulmonary function tests with values <80% of core study baseline.
13. Severe liver impairment or chronic liver disease.
14. Positive screening for serological markers for hepatitis A, B, C and E indicating acute or chronic infection:
  - anti-hepatitis A virus IgM,
  - hepatitis B surface antigen and/or anti-hepatitis B core antigen IgM,
  - anti-hepatitis C virus IgG or IgM,
  - anti-hepatitis E virus IgM (if positive IgG: do hepatitis E virus-RNA polymerase chain reaction: if negative, patient can be included).

[figure not shown]
Note: The following patients, assuming they have normal aminotransferase activities, can be included in the trial:

- those testing positive for hepatitis B surface antibody, indicating hepatitis B immunization - OR-
- those testing positive for anti-hepatitis B core antigen IgG, indicating a cured hepatitis B - OR-
- those testing positive for anti-hepatitis A virus IgG, indicating a cured hepatitis A.

#### **Investigational therapy:**

All patients will receive open-label fingolimod 0.5 mg, taken p.o. once daily.

#### **Study design:**

This study uses an open-label, multi-center, single treatment arm design allowing patients participating in the fingolimod multiple sclerosis clinical development program to enroll to collect additional long-term safety, tolerability, efficacy, and health outcomes data.

This study has two parts:

- Part One, collecting long-term safety, tolerability, efficacy, and health outcomes data through approximately 30-Jun-2016, and
- Part Two\*, collecting limited safety data until approximately 30-Jun-2018, in a subset of patients participating in Part One, and other eligible patients from ongoing fingolimod trials (e.g., CFTY720D2312).

\*Eligibility for Part Two is defined as prior fingolimod study patients who are unable to obtain fingolimod outside a clinical trial.

By June 2016, investigators must determine commercial Gilenya eligibility for all active study patients (i.e., reimbursed for commercial Gilenya). Patients able to obtain commercial Gilenya will then have their End of Study (Part One) visit and exit the study, regardless of their post-study treatment decision (i.e., continuing on Gilenya commercially or transitioning to another treatment option). Patients discontinuing or completing the study at Part One who do not continue on commercial Gilenya must return for two follow-up study visits, 3-months and 6-months post-last dose of fingolimod. Patients who choose to continue on commercial Gilenya outside the study are exempted from the follow-up visits.

[figure not shown]
Patients not eligible for reimbursed, commercial Gilenya will be offered continued study participation in Part Two until their scheduled study visit closest to 30-Jun-2018 (+/- 30 day visit window), with a reduced assessment schedule (see Table 6-2), for the purpose of collecting additional long-term safety and tolerability data in support of the primary study objective. Patients discontinuing or completing the study after entering Part Two who do not continue on commercial Gilenya must return for one follow-up study visit, 3-months post-last dose of fingolimod. Patients who choose to continue on commercial Gilenya outside the study are exempted from the follow-up visit.

**Safety assessments:**

- Physical/neurological examination
- Vital signs
- Laboratory blood evaluations
- Eye exam by treating physician
- ECG
- Ophthalmologic Exam/Optical coherence tomography (OCT) by ophthalmologist, if clinically indicated
- Skin assessments, if clinically indicated
- Pulmonary function testing, if clinically indicated

**Efficacy assessments:**

- MS Relapse
- Expanded Disability Status Scale (EDSS)
- Magnetic Resonance Imaging (MRI)
- Multiple Sclerosis Functional Composite (MSFC)

**Data analysis:**

Unless otherwise specified, the following pertains to the entire study (Study Parts One and Two).

Long-term safety will be assessed based on adverse events (AEs), laboratory and vital signs as well as other investigations performed when clinically indicated. Analysis of the safety variables will be conducted on the safety set.

Incident rates (IRs) of adverse events per 100 patient-years will be summarized by highest assigned fingolimod dose (fingolimod 0.5 mg/day and any dose of fingolimod).

To further evaluate the risk with longer fingolimod exposure duration, IR if adverse events reported with different fingolimod exposure durations will be compared.

In addition, the incidence of adverse events (new or worsened from the long-term extension baseline) reported during the long-term extension will be summarized by primary system organ class and preferred term as frequency count and percentage of patients with adverse events.

The incidence of death, serious adverse events (SAEs), AEs leading to discontinuation, and other significant AEs will be summarized separately by primary system organ class and preferred term.

Laboratory data will be summarized using summary statistics of raw data and change from baseline values. For liver function tests, the frequencies and percentages of patients with elevations of 1, 2, 3, 5, and 10 times upper limit of normal will be summarized by visit (Study Part One only).

Vital sign data will be summarized as descriptive statistics for change from baseline value. The incidence rates of notable vital sign abnormalities will be summarized.

Summary statistics for ECG parameters (including pre-dose ECG for patients who have this evaluation done) will be summarized by visit. Incidence of abnormal ECGs by type of abnormality will be presented.

The incidence of macular edema events will be summarized as frequency distributions. The patient data listing will also be provided.

Pulmonary function test data (FEV1, FVC, and DLCO, percentage of predicted value for these three variables, and smoking status) will be summarized.

The skin assessment will be summarized based on abnormal findings.

The safety data will also be summarized by subgroups for the supportive safety analysis purpose.

The safety data obtained after discontinuation of the study drug will be summarized.

Descriptive statistics (along with change from baseline to post-baseline visit, where appropriate) will be presented for the following variables: Annual Relapse Rate (ARR), time to relapse (including HR), absolute EDSS scores, time to EDSS scores of 4, 6, 7, time to 6-month confirmed disability progression, absolute MSFC scores

[REDACTED]

[REDACTED]

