- The use of fingolimod in women who are or may become pregnant should only be considered if the potential benefit justifies the potential risk to fetus. Animal studies have shown reproductive toxicity including fetal loss and organ defects, notably persistent truncus arteriosus and ventricular septal defect. Furthermore, the receptor affected by fingolimod (sphingosine-1-phosphate receptor) is known to be involved in vascular formation during embryogenesis. The data available from the use of fingolimod in pregnant women are too limited to draw conclusions on safety of fingolimod in pregnancy. Since it will take approximately 2 months to eliminate the compound from the body upon stopping treatment, risk potential to the fetus may persist and contraception should be pursued during that period. The risk of teratogenic effects of fingolimod is being further addressed in a specific pregnancy registry. Fingolimod is excreted in milk of treated animals during lactation. Because of the potential for serious adverse drug reactions in nursing infants from fingolimod, women receiving fingolimod should not breast feed.
- The safety and tolerability profile did not change over time, as determined in the pooled data of the phase II and III studies and their respective open-label extension studies. In particular, the incidence of malignancies and serious infections did not increase over time. Further long-term data are however needed to better estimate the incidence of rare or time-dependent adverse events.

The current data showed no significant difference on efficacy between the fingolimod 1.25 mg/day and the 0.5 mg/day doses in phase III studies. Fingolimod 0.5 mg/day was associated with an overall more favorable risk/benefit profile than fingolimod 1.25 mg/day. Based on these data, the dose of fingolimod chosen for registration and for further clinical development is 0.5 mg/day.

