## **9.4 Analysis of the primary variable(s)**

### **9.4.1 Variable**

Long-term safety will be assessed based on adverse events (AEs), laboratory and vital signs as well as other investigations performed when clinically indicated.

Analysis of the safety variables will be conducted on

[figure not shown]
- Safety set: for any analyses including data collected during the long-term follow up study only
- Fingolimod safety set: for analyses including data from first dose of fingolimod in the original core/extension study, if there is any, and in the long-term follow up study.

Given the nature of the design, the data will be presented using descriptive statistics and no inferential analyses are planned.

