#### **9.6 Sample size calculation**

Given that this is a long-term extension study with primary descriptive purpose, no formal sample size calculation will be used to determine enrollment in this study. The sample size is defined by the number of patients coming from ongoing/new core/extension trials that meet the inclusion and exclusion criteria. It is estimated that about 5000 patients will be enrolled in this trial.

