## **9.8 Interim analyses**

Periodic interim safety analyses to support regulatory updates and interim reports may be warranted.

As this is an open-label, multi-center, single treatment arm long-term safety and tolerability study without formal hypothesis tests, there is no relevance on blinding or alpha-adjustment.

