8.1.4 MS relapses analyses

MS relapses analyses will be conducted on the fingolimod full analysis set. All analyses will be done for all relapses (confirmed and unconfirmed) and for confirmed relapses.

A summary of ARRs will be presented by time period (cumulative time intervals: ‘Month 0 to Month 6’, ‘Month 0 to Month 12’, ‘Month 0 to Month 24’, ‘Month 0 to Month 36’, ... incremented by 1 year for each successive interval, plus ‘Month 0 to end of study treatment’ and ‘Month 0 to end of follow-up’) from first dose of fingolimod among all studies. The summary will include number of patients summarized, number of relapses, time in study (days), and group level ARR. In addition, model based estimates of ARR and corresponding two-sided 95% confidence interval will be obtained by fitting a negative binomial regression model adjusted for the number of relapses in the last two years prior to

enrolment in the core study and EDSS score at first dose of fingolimod baseline, with the logarithm of the time in study as the offset variable.

A summary of relapse characteristics will be displayed by time period (consecutive yearly intervals: 'Month 0 to Month 12', 'Month 12 to Month 24', etc., plus 'End of study treatment to End of follow-up') from first dose of fingolimod among all studies. Relapse characteristics will be summarized at a patient level (the number and percent of patients with at least one relapse type) and at a relapse event level (the number and percent of a particular type of relapse out of the total number of relapses). The types of relapses being summarized include: relapses which affect daily activities, relapses which require steroids, and relapses which require hospitalization.

The time to first onset of relapse from first dose date of fingolimod among all studies will be analysed. Specifically, the number of patients at risk, the cumulative number of patients with relapse, the Kaplan-Meier (KM) estimate of the percent of patients without relapse and corresponding standard error and two-sided 95% CI will be provided at each yearly time point (1 year = 360 days). Patients with no relapse, patients for whom follow-up ends before a confirmed relapse occurs, and patients who drop out prior to the relapse will all be censored, i.e. the time to event for these patients will be the time in study (from first dose of fingolimod among all studies to last available visit/evaluation date across all panels).

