9.1.2.2 Adverse events during the fingolimod treatment period

Unless otherwise specified, all non-serious adverse events with onset on or after first dose date of fingolimod among all studies to last dose date of fingolimod + 45 days are included. All serious adverse events (SAEs) with onset on or after the first dose date of fingolimod among all studies are also included in the summaries. Also, unless otherwise specified, adverse events will be summarized for the fingolimod safety set, by primary system organ class and preferred term, and will show the number of patients with at least one adverse event and the incidence rate of adverse events per 100 patient-years in each SOC or PT category.

The AE incidence rate (IR) is calculated per 100 patient-years. IR is defined as: the number of patients experiencing at least one event in a particular category, over the total patient-years of the “at risk” population for that event multiplied by 100. An underlying Poisson process for incidence rate within treatment group is assumed.

To calculate the total patient-years (time at risk) of the “at risk” population:

1. For patients who have a particular AE category, sum the number of days from first dose date of fingolimod among all studies to the first occurrence of that particular AE category

2. For patients who did not have a particular AE category, sum the number of days from first dose date of fingolimod among all studies to last dose date of fingolimod + 45 days.
3. Add the time at risk for patients who had a particular AE category with the time at risk for patients who did NOT have a particular AE category. This is the total time at risk of that AE category.
4. Divide the total time at risk by 365.25.

Incidence rate of adverse events will be presented for the fingolimod safety set and for the subgroup of fingolimod safety set patients from phase II/III studies, by SOC and PT. Incidence rate of AEs, excluding AE listed in the core data sheet, will be presented by PT. Incidence rate of AEs that fulfill the risk search term (defined in the case retrieval sheet) will be presented by risk name and lower level terms. Similarly, all above indicated AE IR summaries will be conducted for SAEs.

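### The primary adverse-event incidence rates and yearly percentages are planned with no measure of precision, so the tables would not show how uncertain small and zero counts are.

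*Protocol*

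**What the plan says.** The primary objective is long-term safety and tolerability (protocol 2.1). The synopsis states that "Incident rates (IRs) of adverse events per 100 patient-years will be summarized by highest assigned fingolimod dose". Protocol 9.4.1, which covers the safety variables, adds: "Given the nature of the design, the data will be presented using descriptive statistics and no inferential analyses are planned". On size, protocol 9.6 says "no formal sample size calculation will be used to determine enrollment in this study".

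SAP Part I, 9.1.2.2, fixes the content of the incidence tables: they "will show the number of patients with at least one adverse event and the incidence rate of adverse events per 100 patient-years", by system organ class and preferred term. It also plans rates for the risk-search terms. The distributional statement is "An underlying Poisson process for incidence rate within treatment group is assumed". SAP Part 2, 9.1.2.1.2, repeats the definition and the Poisson statement for events from the first Part 2 dose. It presents rates by preferred term, names no count column and plans no risk-term rates.

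For exposure duration, both SAPs (Part I 9.1.2.2; Part 2 9.1.2.2) use the number and percentage of patients with an event in each 360-day interval. Risk-search terms are included there in both parts.

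None of these outputs carries a standard error or an interval. By contrast, SAP Part I 8.1.4 plans "model based estimates of ARR and corresponding two-sided 95% confidence interval". Two-sided 95% intervals are also planned for the T2-lesion rate, brain volume change and its annualized rate, and the Kaplan-Meier estimates for relapse, EDSS thresholds and confirmed progression (8.1.4, 8.2.1, 8.2.3, 8.2.4, 8.3.2, 8.3.3). SAP Part 2 8.1.4 does the same for relapse.

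**The concern.** Protocol 1.1 explains why the study continues: "Further long-term data are however needed to better estimate the incidence of rare or time-dependent adverse events". Rare events mean small counts, and a bare rate says least about its own reliability exactly there. A zero row is the extreme case. The useful statement is the upper bound on the rate, and the planned tables give none. Time-dependent events raise the same problem in the yearly percentages, where later intervals hold fewer patients.

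A Poisson model is assumed for the rates but no planned output in these documents draws on it, while the secondary estimates are shown with their precision. At stake is how the safety tables are read. A few cases may be taken as a signal, or an empty row as reassurance, without the range of rates that the data allow.

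**Working it through.** The plan states no interval, power or precision target for adverse events, so there is no figure to reproduce. The size of the gap can be illustrated.

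**Inputs**
- Patient-years (PY) are assumptions, because the documents give no at-risk total for this study. The central value is 16,500 PY, the whole-programme exposure at 29-Feb-2012 (protocol 1.1). The range uses the roughly 4,150 enrolled patients (Amendment 11 rationale): 1 year each gives 4,150 PY, and 6 years each gives 4,150 × 6 = 24,900 PY.
- k is the number of patients with the event.

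**Formula** (exact Poisson, 95%, per 100 PY)
- lower = 100 × χ²(0.025; 2k) / (2 × PY), taken as 0 when k = 0
- upper = 100 × χ²(0.975; 2k+2) / (2 × PY)

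The limits for the count itself are 0 to 3.69 for k = 0, and 0.62 to 8.77 for k = 3.

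| k | 4,150 PY | 16,500 PY | 24,900 PY | upper/lower |
|---|---|---|---|---|
| 0 | 0 (0 to 0.089) | 0 (0 to 0.022) | 0 (0 to 0.015) | not defined |
| 3 | 0.072 (0.015 to 0.211) | 0.018 (0.004 to 0.053) | 0.012 (0.003 to 0.035) | 14.2 |
| 5 | 0.120 (0.039 to 0.281) | 0.030 (0.010 to 0.071) | 0.020 (0.007 to 0.047) | 7.2 |
| 10 | 0.241 (0.116 to 0.443) | 0.061 (0.029 to 0.111) | 0.040 (0.019 to 0.074) | 3.8 |
| 20 | 0.482 (0.294 to 0.744) | 0.121 (0.074 to 0.187) | 0.080 (0.049 to 0.124) | 2.5 |

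Exposure cancels in the last column, so the 14-fold span for 3 cases does not depend on the assumed totals.

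**Yearly percentages.** Take the 0.4% macular edema figure in protocol Appendix 7 and assumed interval sizes. Exact binomial 95% limits are 0.05% to 1.44% for 2 of 500, 0.11% to 1.02% for 4 of 1,000, and 0.24% to 0.66% for 17 of 4,150. The three rows would print almost the same percentage.

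**Can a reader rebuild the interval?** In Part I, for non-zero rows, roughly. With 3 cases and a printed rate of 0.0182, PY = 300/0.0182 ≈ 16,484 and the limits are 0.004 to 0.053. If the rate is printed as 0.02, PY = 300/0.02 = 15,000 and the limits become 0.004 to 0.058. A zero row cannot be inverted. The exposure totals in section 6.1 of each SAP are only a stand-in, because they remove interruptions, whereas time at risk does not and runs to last dose + 45 days. In Part 2 the main occurrence tables count events from the first fingolimod dose in any study (9.1.2.1), so their counts are not the numerator of the Part 2 rate.

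**The case against.** The strongest reply is that the sponsor follows its own plan. Protocol 9.4.1 makes the safety analysis descriptive, and 9.8 says that without formal tests "there is no relevance on blinding or alpha-adjustment". Efficacy falls under 9.5, which separately plans model-based estimates. This stands: a reader might infer that the efficacy intervals are produced under the same no-inference statement and that the plan contradicts itself, but that statement sits in the safety section only. The contrast shows that intervals are feasible here, not that a rule is broken. An interval is also estimation, so 9.4.1 does not rule it out.

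Second, Part I prints the count beside the rate, so a small number is visible and an approximate interval can be derived. This stands for non-zero Part I rows. It is weaker for zero rows and for Part 2, where no count column is named.

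Third, unadjusted intervals on every preferred term could themselves invite false signals. This stands, and it limits where they should be used.

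Three further readings are tempting and not supported:
- That differences between doses cannot be judged. The 0.5 mg column is contained in the any-dose column (SAP Part I 2.1), so no contrast of separate doses is planned, and an interval on each column would not create one.
- That Part I and Part 2 rates would be miscompared. No such comparison is planned, the two rates start from different first doses, and any ratio between their limits would mainly reflect the patient-years assumed for each.
- That small differences cannot be told from chance for want of an interval. With equal exposure, 6 versus 2 cases gives a rate ratio of 3.0 (0.54 to 30.4). That is compatible with chance with or without an interval in the table; the interval only displays it.

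**Conclusion.** The point holds as a gap in presentation. The rates serving the primary objective, and the yearly percentages that address time-dependence, have no planned measure of precision in the protocol or either SAP part. The consequence is largest for counts of about 0 to 5: a 14-fold span for 3 cases at any exposure, and for 0 cases an upper limit of 0.022 per 100 PY at 16,500 PY (0.015 to 0.089 over the assumed range).

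No stated figure or rule is wrong. The patient-year totals are illustrations, and rare events are named in the background rather than in the formal objective. The documents cite other analysis modules that are not available here, so the conclusion covers only what these texts plan. The change is worth making because it is cheap and lets the study state upper bounds for rare events.

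**What to change.** 1. In SAP Part I 9.1.2.2 and SAP Part 2 9.1.2.1.2, at least for SAEs in both parts and for the risk-search terms in Part I, show three items with each rate: patients with the event, patient-years at risk, and the exact Poisson 95% interval from the formula above. Keep zero-event rows for the Part I risk terms.
2. In section 9.1.2.2 of both parts, add exact binomial 95% intervals to the yearly-interval percentages. Note beneath the table that patients count in an interval after one day of treatment in it, so not all are observed for the full 360 days.
3. For SAE rates, count numerator and time at risk over the same window. At present SAEs count without an end limit after the first dose, while time for event-free patients stops at last dose + 45 days. An interval computed on that mismatch would look more exact than it is.
4. State that all these intervals are descriptive and unadjusted for multiplicity.

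Cost: a few columns in existing tables, since patient counts and at-risk time are already derived; item 3 also needs a changed window in the SAE derivation. The downside is wider tables and many unadjusted intervals, which is why the minimum scope is SAEs and risk terms rather than every preferred term.
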